A reduction of 15% or more in the primary endpoint is regarded as clinically significant. Assuming an alpha significance level of 0.05, a statistical power of 80% and an expected number of NIT/ICA of 0.94 per patient in the standard care group, a sample size of 314 patients in each arm is needed to ascertain superiority of the intervention, in this case an absolute reduction in the primary endpoint of 0.17 NIT/ICA per patient, i.e. number of NIT/ICA.

The expected number of NIT/ICA of 0.94 in the control group and 0.77 in the intervention group is based on the following sequence of assumptions:

- No. of first NITs: n=760 in the control group (all patients with DF-score 15-85%) and n= 610 in the intervention group (all patients with a CAD-score not ruling out CAD + 20% of patients with a CAD-score ruling out CAD).
- No. of second NITs: 10% of first NIT; n=76 in the control group and n=61 in the intervention group.
- No. of ICAs: 10% of total population; n=100 in each group.

Note: the patient pathway is expected to change only slightly due to the updated ESC 2019 guidelines (Knuuti *et al.* 2019). Current data indicates that the number of patients in each arm will increase to 521 for the primary endpoint; which stays within the total number of 2000 patients as described below.

Given the abovementioned assumptions, the mean number of investigations (NITs and ICAs combined) per patient will be 0.94 in group 1 and 0.77 in group 2. A sample size of 314 patients in each arm will then provide 80% power for testing superiority in terms of number of diagnostic procedures for the group with CAD-score stratification compared to the group with DF-score only stratification, at an alpha significance level of 0.05.

The study allows for some degree of cross-overs where patients with PTP or CAD-score ruling out CAD instead are crossed-over to a NIT. The power calculation simulates a worst-case scenario where the two

groups (control and intervention group) have the lowest expected difference in number of diagnostic procedures; 0% of patients with low PTP ruling out CAD (Diamond-Forrester(DF) <15 %) crossed-over to NIT in the control and 20% of patients with a CAD-score ruling out CAD in the intervention group crossed-over to NIT.

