5.2. Statistical Hypothesis, Model and Method of Analysis

Statistical Hypothesis

The statistical null hypothesis is a PTP plus CAD-score guided rule-out strategy is inferior in terms of safety outcomes MACE (π) in patients with symptoms suggestive of stable CAD at one year when using a pre-specified non-inferiority margin (δ) as compared to a standard PTP guided strategy.

$$H_0 = \pi_{PTP+CAD-score} - \pi_{PTP} \geq \delta$$

The alternate hypothesis is that a PTP plus CAD-score guided rule-out strategy is non-inferior to a standard PTP-guided strategy in terms of MACE in patients with symptoms suggestive of stable CAD at one year when using a pre-specified non-inferiority margin (δ).

$$H_A = \pi_{PTP+CAD-score} - \pi_{PTP} < \delta$$

Statistical Model and Method of Analysis

The absolute risk difference between treatment groups will be compared to a non-inferiority margin (δ) of 1.5% using a two-sided 95% confidence interval applying a continuity-corrected modification of the Wilson's score method. Based on previous studies (Therming *et al* 2018) the obstructive CAD prevalence is expected to be 6.5% and the event rate in each group is expected to be 1.3% at 1-year FU.

Moreover, data will be analyzed using stratified proportional hazard Cox regression and visually by Kaplan Meier curves.

Sample size

A sample size of 1914 provides 90% power with an alpha significance level of 0.05 for testing non-inferiority in terms of MACE between the control and intervention group.

This sample size calculation is based on the hypothesis of non-inferiority in terms of MACE in the group of patients with DF-score and CAD-score stratification prior to NIT compared with the group of patients with standard care strategy of DF-score stratification prior to NIT. It is assumed that in the control group, 50% of the patients with a DF-score <15% are ruled out of obstructive CAD without further testing, and 50% are referred for further testing. Based on previous studies (Therming *et al* 2018) the obstructive CAD prevalence is expected to be 6.5% and the event rate in each group is expected to be 1.3% at 1-year FU. The non-inferiority margin is set to 1.5%.

The assumed annual MACE event rates for different patient categories are:

- Clean arteries (CACS=0 and no stenosis): 0.4%

- Non-obstructive CAD: 1.2%
- Diagnosed CAD: 6.9%
- Unobserved CAD: 10.0%

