The diagnostic performance of the CAD-score and the DF-score is assumed to be 88.7% and 96.7%, respectively, for sensitivity and 41.5% and 17.9%, respectively, for specificity (Schmidt *et al* 2019). The weighted average for sensitivity and specificity of the combined NIT battery is assumed to be 85.6% and 80.2%, respectively, assuming a distribution of exercise ECG, stress echo, MPI and CCTA as in Therming *et al* 2018 and diagnostic performance for each test as in the ESC 2013 guidelines (Montalescot *et al* 2013).

With the abovementioned assumptions a sample size of 1914 provides 90% power for testing non-inferiority in terms of MACE between the two testing strategies, at an alpha significance level of 0.05.

Note: the MACE event rate is not expected to change due to the updated ESC 2019 guidelines (Knuuti *et al*. 2019), thus the power calculation related to the MACE endpoint remains unchanged.

6. Other Secondary Objectives

Other secondary objectives are to compare the two treatment arms with respect to:

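### SAP 5.2 claims 90% power for MACE non-inferiority with 1914 patients; under its own two-sided 95% continuity-corrected interval the power is about 74%

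*SAP*

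**What the plan says.** The key secondary objective is non-inferiority on one-year MACE, with a one-directional alternative: the risk difference, intervention minus control, is below the margin. SAP section 5.2 fixes these points:

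- **Decision rule.** The risk difference is compared with a 1.5% margin "using a two-sided 95% confidence interval applying a continuity-corrected modification of the Wilson's score method".
- **Event rate.** The plan assumes that "the event rate in each group is expected to be 1.3% at 1-year FU".
- **Power.** The opening line of the sample-size text reads "A sample size of 1914 provides 90% power with an alpha significance level of 0.05 for testing non-inferiority in terms of MACE". The closing paragraph repeats that "a sample size of 1914 provides 90% power for testing non-inferiority in terms of MACE between the two testing strategies". Neither says whether alpha is one- or two-sided.

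A final note in 5.2 says the MACE power calculation still stands after the 2019 guideline update. Section 1 gives 1:1 randomisation and about 2000 patients, and section 4.2 also refers to the total of 2000 ("which stays within the total number of 2000 patients as described below"). So 1914 must be the two-arm total, 957 per arm.

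**The concern.** Non-inferiority is declared when the upper limit of a two-sided 95% interval lies below the margin. That is a test at one-sided 2.5%. The planned interval is also more conservative than the usual normal approximation, because it is a score-type interval with a continuity correction. A power statement for this endpoint should reflect both features, and the stated 90% appears to reflect neither.

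MACE is the safety check on a strategy meant to reduce testing. Its 1914 is the larger of the two sample-size requirements (the updated primary-endpoint figure in 4.2 is 521 per arm) and lies close to the planned total. If the real power is well below 90%, an inconclusive safety result is much more likely than the plan says, even with truly equal strategies, and readers of such a result would be misled about how likely it was.

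**Working it through.** **Inputs, all from SAP sections 1 and 5.2:** p = 0.013 in both arms; margin δ = 0.015; 1:1 allocation; 957 per arm; stated power 90%; decision by two-sided 95% interval.

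**Step 1: reproduce the plan's figure.** The unpooled normal approximation is

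n per arm = (z_α + z_β)² × 2p(1−p) / δ²

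with 2p(1−p)/δ² = 0.025662 / 0.000225 = 114.05.

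- One-sided 0.05: (1.645 + 1.282)² × 114.05 = 976.7, so 977 per arm, 1954 in total. This is within 3% of 1914.
- One-sided 0.025: (1.960 + 1.282)² × 114.05 = 1198.4, so 1199 per arm, 2398 in total. This does not reproduce 1914.

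Solving for the rate that gives exactly 957 per arm yields about 1.27% at one-sided 0.05, which rounds to the stated 1.3%. At one-sided 0.025 it yields about 1.04%, which does not. A Farrington-Manning score calculation gives 2223 and 2754 in total at the two levels, so it does not explain 1914 either.

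**Step 2: power at 957 per arm, same approximation.** The standard error is √(0.025662/957) = 0.005178, and δ/SE = 2.897.

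- One-sided 0.05: Φ(2.897 − 1.645) = 89.5%.
- One-sided 0.025: Φ(2.897 − 1.960) = 82.6%.

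**Step 3: power under the planned interval.** For a risk difference, the method named in 5.2 is read as the Newcombe hybrid score interval with continuity correction. Non-inferiority is declared when

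(p₁ − p₂) + √[(u₁ − p₁)² + (p₂ − l₂)²] < 0.015

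Here p₁ and p₂ are the observed proportions (intervention, control), u₁ is the upper continuity-corrected Wilson limit for the intervention arm, and l₂ is the lower one for control. Power is the sum of the binomial probabilities of all event-count pairs that meet the rule.

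| Rule, 957 per arm, 1.3% in both arms | Power |
|---|---|
| Normal approximation, one-sided 0.05 | 89.5% |
| Normal approximation, one-sided 0.025 | 82.6% |
| Wald two-sided 95%, exact enumeration | 83.1% |
| Newcombe two-sided 95%, no continuity correction | 77.7% |
| **Newcombe two-sided 95%, continuity-corrected (planned)** | **73.6%** |
| Newcombe two-sided 90%, continuity-corrected | 83.6% |

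The level costs about 7 points (89.5% to 82.6%) and the conservative interval about 9 more (82.6% to 73.6%).

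**Step 4: sensitivity of the planned rule.** Event rates other than 1.3%, and the 5% missing outcomes, are assumptions.

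| Rate in both arms | 1914 patients | 2000 patients |
|---|---|---|
| 1.0% | 82.2% | 84.7% |
| 1.3% | 73.6% | 76.2% |
| 1.4% | 70.8% | 73.6% |

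- Rounding of the 1.3% (1.25% to 1.35%) moves power at 1914 only between 75.0% and 72.2%.
- With 5% missing outcomes (909 per arm) power is 71.4%.
- Power of 90% at 1914 needs a rate of about 0.74% or lower.
- At 1.3%, about 1400 per arm (2800 in total) would be needed for 90%.

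**Step 5: validity.** With the true difference equal to 1.5 points and control rates of 0.8% to 2.0%, the planned rule declares non-inferiority with probability between 1.6% and 1.9%, below the nominal 2.5%.

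**The case against.** The strongest reply is that 5.2 never calls its alpha one-sided. Read as two-sided, 0.05 agrees with a two-sided 95% interval, and the one-sided reading is inferred by working back from 1914. That is fair as to the wording. It does not help the claim, because on the two-sided reading the simple formula already gives 82.6%, not 90%.

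Second, sizing by normal approximation and analysing with a more conservative interval is common, and the SAP does not say that 1914 was computed with the planned interval. This is why the two steps are kept apart above. The first 7 points follow from the level alone; the other 9 depend on the interval.

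Third, the two-sample form of the interval is not named, and section 1 says all analyses are stratified by site and PTP, without saying how this interval would be stratified. So 73.6% rests on the Newcombe reading and an unstratified analysis. The Newcombe hybrid is the natural reading, and none of the two-sided 95% versions computed reaches 90%. Stratification was not modelled, and the replacement figure should say so.

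Fourth, the disease-category model behind the 1.3% is only partly shown, so the unrounded arm rates cannot be rebuilt. Rounding of a common rate does not close the gap. A slightly higher intervention rate would widen it (1.34% against 1.30% gives 70.5%).

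Finally, the consequences are limited: this is a key secondary endpoint, and the analysis stays valid. That bears on severity, not on whether the statement is correct.

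**Conclusion.** The concern holds. The 90% stated twice in 5.2 is not the power of the decision rule in the same section. It matches, to within half a point, a one-sided 5% normal approximation, which is a more lenient test. Under the planned rule the power at 1914 is about 74%, so the chance of missing non-inferiority when the arms are equal is about 26% instead of 10%. Full enrolment of 2000 raises power only to about 76%.

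These figures assume 1.3% events in both arms, the Newcombe form of the interval, no dropout and no stratification. The error lies in the planning statement alone: there is no added risk of a false safety claim. It should be fixed, but it does not undermine the analysis.

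**What to change.** In both places in the sample-size text of 5.2:

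- State alpha as one-sided 0.025, matching the two-sided 95% interval.
- Replace 90% with about 74% at 1914 patients and about 76% at 2000, for a 1.3% rate in both arms.
- Add a range over event rates, for example about 82% at 1.0% to 71% at 1.4% for 1914 patients.
- Name the two-sample form of the interval, and say that the figures assume equal arms, no dropout and no stratification.

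If the sponsor wants to keep the planning history, the 90% can stay as a historical figure, labelled with the method and sidedness that the sponsor confirms were used, and with the power of the planned rule beside it.

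The interval, the 1.5% margin and the number of patients should not change. In particular, the interval should not be loosened to rescue the power claim; a 90% interval by the planned method would give only 83.6% anyway. The cost is a wording change in two places and a less favourable stated power.

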6.1. Symptoms

6.1.1 Objective

To investigate if chest pain differs in the two treatment arms

6.1.2 Endpoint

Change in chest pain from baseline to 3 months, and 1 year, respectively, after randomization. Chest pain symptoms will be assessed by the Seattle Angina Questionnaire (SAQ).

6.1.3 Statistical Hypothesis, Model and Method of Analysis

The statistical null hypothesis is that there is no difference between the two treatment arms with regards to symptoms. Within treatment group comparisons will be made with Wilcoxon signed rank test. Between treatment group comparisons will be made with Mann-Whitney U test.

6.2. Investigations

6.2.1 objectives

- A. To investigate if the number of first NIT differ in the two treatment arms 1 year after randomization.
- B. To investigate if the number of downstream tests differ in the two treatment arms 1 year after randomization. Downstream tests defined as all NITs and ICA to detect CAD performed after a) PTP and first standard non-invasive testing and b) PTP, CAD-score and first non-invasive testing,

respectively, in the two groups. The term PTP refers to the DF-score for patients enrolled according to protocol version 3.0 and to the PTP in the ESC 2019 guidelines for patients enrolled according to protocol version 4.0 and 5.0, respectively.

- C. To investigate if the number of ICA differ in the two treatment arms 1 year after randomization.
- D. To investigate if the number of negative ICA differ in the two treatment arms 1 year after randomization. Classification of ICA results as positive, negative, or inconclusive will be done at each individual site according to local criteria/guidelines.
- E. To investigate if the number of repeat referrals differ in the two treatment arms 1 year after randomization.
- F. To investigate if the number of NIT performed after revascularization in the two treatment arms 1 year after randomization.

6.2.2 endpoints

- A. Difference between the two treatment groups in the number of first NIT, assessed at 1 year after randomization.
- B. Difference between the two treatment groups in the number of downstream tests, assessed at 1 year after randomization.
- C. Difference between the two treatment groups in the number of invasive coronary angiographies, assessed at 1 year after randomization.
- D. Difference between the two treatment groups in the number of negative invasive coronary angiographies, assessed at 1 year after randomization.
- E. Difference between the two treatment groups in the number of repeat referrals, assessed at 1 year after randomization.
- F. Difference between the two treatment groups in numbers of NIT performed after revascularization, assessed at 1 year after randomization.

6.2.3 Statistical Hypothesis, Model and Method of Analysis

- A. The statistical null hypothesis is that there is no difference between the two treatment arms with regards to the number of first NIT differ in the two treatment arms 1 year after randomization.
- B. The statistical null hypothesis is that there is no difference between the two treatment arms with regards to the number of downstream tests differ in the two treatment arms 1 year after randomization.

- C. The statistical null hypothesis is that there is no difference between the two treatment arms with regards to the number of invasive coronary angiographies differ in the two treatment arms 1 year after randomization.
- D. The statistical null hypothesis is that there is no difference between the two treatment arms with regards to the number of negative invasive coronary angiographies differ in the two treatment arms 1 year after randomization.
- E. The statistical null hypothesis is that there is no difference between the two treatment arms with regards to the number of repeat referrals differ in the two treatment arms 1 year after randomization.
- F. The statistical null hypothesis is that there is no difference between the two treatment arms with regards to the numbers of NIT performed after revascularization 1 year after randomization.

Comparisons of categorical data will be done using Fisher's exact test.

6.3. Diagnosis

6.3.1 Objectives

- A. To investigate if the time to rule-out CAD differ in the two treatment arms 1 year after randomization.
- B. To investigate if the time to diagnosis of CAD differ in the two treatment arms 1 year after randomization.

6.3.2 Endpoints

- A. Difference between the two treatment groups in time to rule-out CAD, assessed at 1 year after randomisation. Time to rule-out is assessed as the period from randomisation until the first test that rules out stable CAD.
- B. Difference between the two treatment groups in time to diagnosis of CAD, assessed at 1 year after randomisation. Time to diagnosis is assessed as the period from randomisation until the first test that leads to the final diagnosis.

6.3.3 Statistical Hypothesis, Model and Method of Analysis

- A. The statistical null hypothesis is that there is no difference between the two treatment arms with regards to the time to rule-out CAD differ 1 year after randomization.
- B. The statistical null hypothesis is that there is no difference between the two treatment arms with regards to the time to diagnosis of CAD differ 1 year after randomization.

Time-to-event data will be analysed using Nelson-Aalen nonparametric estimator and stratified proportional hazards Cox regression.

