6.5.1 Objectives	13
6.5.2 Endpoints.....	14
6.5.3 Statistical Hypothesis, Model and Method of Analysis	14
6.6. Quality of Life	14

6.6.1 Objective.....	14
6.6.2 Endpoint	15
6.6.3 Statistical Hypothesis, Model and Method of Analysis	15
7. Sensitivity Analysis.....	15
8. Missing Data	15
9. References	15

1. Background and Study Design

The FILTER-SCAD trial is a randomized, controlled, multicentre, superiority trial with two parallel groups investigating the use of the acoustic measured risk score (CAD-score) for obstructive coronary artery disease (CAD) for ruling out CAD as compared to current standard diagnostic strategy in patients with symptoms suggestive of CAD.

Approximately 2000 patients with symptoms suggestive of CAD referred for outpatient assessment are expected to be enrolled at 5 study sites in Denmark and 1 in Sweden. The subjects will be randomized 1:1 to either 1) standard diagnostic strategy i.e. pre-test probability (PTP) stratification followed by non-invasive test (NIT), if indicated (control group), or (2) PTP plus CAD-score stratification followed by NIT, if indicated (intervention group). Randomization is stratified according to study site and PTP. Given the stratified design, all analyzes are carried out stratified by site and PTP.

2. Analysis Datasets

All patients from whom written informed consent are obtained will be included in the **full analysis set (FAS)**. Subjects will be analysed according to the allocated randomization group in accordance with the intention-to-treat principles.

The **per protocol set (PPS)** will include the subjects from the FAS who did *not* have one of the following major protocol violations:

- inclusion criteria not met
- exclusion criteria met
- no PTP calculation
- no CAD-score measurement (intervention group only).

Patients who did not receive the randomly allocated CAD-score measurement will be included and analysed in the control group (per protocol analysis).

The **screened analysis set (SAS)** will include all screened patients who receive a subject number.

3. Demographics and Baseline Characteristics

Continuous variables will be presented as mean and standard deviation for variables following a normal distribution or as median with interquartile range if showing a skewed distribution. Categorical variables will be presented as frequencies and percentages. Categorical data will be compared using Fisher's exact

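### Time to rule-out: the planned Cox hazard ratio does not say how much sooner CAD is ruled out, and the plan leaves open what counts as a ruling-out test

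*SAP*

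**What the plan says.** SAP section 6.3.2 A defines the endpoint as "Difference between the two treatment groups in time to rule-out CAD, assessed at 1 year after randomisation". It adds: "Time to rule-out is assessed as the period from randomisation until the first test that rules out stable CAD". It does not say whether a PTP or CAD-score result is such a test.

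The null hypothesis in section 6.3.3 A is "no difference between the two treatment arms with regards to the time to rule-out CAD". The only methods named there are: "Time-to-event data will be analysed using Nelson-Aalen nonparametric estimator and stratified proportional hazards Cox regression". The section gives no measure in days, no check of proportional hazards, no alternative if that assumption fails, and no rule for rule-outs at time zero.

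Two other places bear on this. Section 1 states: "Given the stratified design, all analyzes are carried out stratified by site and PTP". Section 4.2 gives the planning counts: "No. of first NITs: n=760 in the control group (all patients with DF-score 15-85%) and n= 610 in the intervention group".

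**The concern.** The Nelson-Aalen estimator gives a cumulative hazard and Cox regression gives a hazard ratio. Neither is a difference in time. A hazard ratio can still summarise a time-to-event comparison well when it is roughly constant. Here the design works against that: the intervention inserts a rule-out step ahead of any NIT, and patients who pass that step follow the same NIT pathway as controls. The arm effect is then an early block of extra rule-outs followed by similar hazards.

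Stratifying by site and PTP does not cure this. It lets the baseline hazard differ between strata but still assumes one constant treatment hazard ratio within them.

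Earlier rule-out is a natural benefit to look for in a rule-out strategy. As planned, the reported number would not tell a reader how large that benefit is. Its direction would also depend on a definition and a data rule that the plan does not give.

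**Working it through.** **1. Planning counts (section 4.2).** Control: (760 + 76 + 100)/1000 = 0.936. Intervention: (610 + 61 + 100)/1000 = 0.771. These reproduce the stated 0.94 and 0.77, so the counts are per 1000 patients. Patients without a NIT: 240/1000 = 24% in control and 390/1000 = 39% in intervention.

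**2. Within the PTP >=15% stratum.** If the same 240 low-PTP patients per 1000 go without NIT in both arms, the score removes 760 - 610 = 150 intervention patients before NIT. That is 150/760 = 19.7%, against 0% in control, so the early hazard ratio in this stratum has no upper bound. Unstratified, the early ratio on the complementary log-log scale is ln(0.61)/ln(0.76) = 1.80.

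**3. After that step.** The inputs are the prevalence and accuracy figures in section 5.2 and the 20% crossover in section 4.2.
- Control: prevalence among DF-positive patients is 0.065 x 0.967/(0.065 x 0.967 + 0.935 x 0.821) = 0.0757. The NIT-negative share is 0.0757 x 0.144 + 0.9243 x 0.802 = 75.2%.
- Intervention: prevalence among those sent to NIT is 0.0757 x (0.887 + 0.2 x 0.113)/0.686 = 0.100. The NIT-negative share is 0.100 x 0.144 + 0.900 x 0.802 = 73.6%.

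The two shares are nearly equal, so later hazards are similar. The treatment hazard ratio is high early and close to 1 afterwards.

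**4. Hazard ratio against days saved.** Assumptions: 1000 per arm; rule-out on day 0 in 39% v 24%; 6.5% of each arm never ruled out; exponential wait to NIT with the same mean w in both arms; no strata. Let m = w(1 - exp(-365/w)) be the mean wait truncated at 365 days. The restricted-mean saving is (0.695 - 0.545) x m = 0.15m.

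| Mean wait (days) | m | Saving (days) | HR, Breslow ties | HR, Efron ties |
|---|---|---|---|---|
| 28 | 28.0 | 4.2 | 1.13 | 1.17 |
| 42 | 42.0 | 6.3 | 1.13 | 1.17 |
| 84 | 82.9 | 12.4 | 1.13 | 1.17 |

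The saving triples and the hazard ratio does not move, because Cox regression uses only the order of the times.

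A second check used a Cox model stratified by PTP, gamma-distributed waits of mean 14, 30 or 60 days, the NIT-negative shares from step 3, and 0, 50 or 90% of NIT-positive patients ruled out by a later test. Hazard ratios ran from 1.14 to 1.19 (SE of the log about 0.05) and savings from 3 to 16 days. With 50% later rule-out, savings of 7.2, 8.8 and 13.7 days went with hazard ratios of 1.17, 1.16 and 1.16.

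**5. Day-0 rule-outs dropped (assumptions of step 4).** The hazard ratio is 0.94 (95% CI 0.84 to 1.05). The restricted-mean difference, intervention minus control, is (545m + 65 x 365)/610 - (695m + 65 x 365)/760 = +7.1, +6.8 and +5.9 days for the three waits. Both measures now point towards control. The stratified check gives hazard ratios of 0.94 to 0.98.

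**6. PTP and CAD-score not counted as tests.** Patients without a NIT then run to day 365. With the shares from step 3 and no later rule-out, the restricted-mean difference is (0.76 x 0.752 - 0.61 x 0.736) x (365 - m) = about +41, +40 and +35 days. The stratified check gives hazard ratios of 0.56 to 0.67. Again both measures point towards control.

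**The case against.** The strongest reply is that the change of direction is not a Cox problem. Steps 5 and 6 bear this out: the restricted mean reverses as well. The cause is the undefined event and the handling of day-0 records, so the reversal is no reason to prefer one model over another.

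A reader might infer that a routine software choice could reverse the finding. The documents do not support that. Breslow and Efron ties give 1.13 and 1.17, which point the same way and differ by less than one standard error of the log hazard ratio (about 0.05). The interval for the hazard ratio of 0.94 includes 1. A starker reversal, 0.88 (0.79 to 0.98), appears only if 39.5% of intervention patients and no controls are ruled out on day 0. That needs 93.5% of controls to be ruled out after a NIT wait, whereas section 4.2 gives only 760 per 1000 a first NIT.

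Other points also carry weight. The difference-between-groups phrasing is the SAP's usual form for an endpoint and does not expressly ask for days. The Cox score test remains a valid test of equal time-to-rule-out distributions. The planned Nelson-Aalen curves would show an early jump. The SAP does not say when the CAD-score is measured, so day 0 is an assumption, although a measurement some days later but still before NIT would also break proportional hazards.

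What remains is that none of the planned outputs gives the size of the difference in time, and that the event is not fully defined.

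**Conclusion.** The point holds as a cheap improvement to an other-secondary endpoint. Proportional hazards is not expected to hold even within strata, because about 20% v 0% of patients in the PTP >=15% stratum are ruled out before any NIT and hazards are similar thereafter. If score rule-out falls at or near randomisation, a hazard ratio of about 1.13 to 1.17 is compatible with a mean saving of 4, 6 or 12 days, so it does not measure how much sooner CAD is ruled out.

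The undefined test and the missing day-0 rule are a separate gap. They can turn the direction of any estimate, whether a hazard ratio or a restricted mean.

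The size rests on the section 4.2 counts and on assumed NIT waits, which the SAP does not give. It does not follow that the planned test is invalid or that Cox must be removed. The primary and key secondary conclusions are unaffected.

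**What to change.** - In section 6.3.2 A, state whether a PTP or CAD-score rule-out counts as the test that ends the interval, applied the same way in both arms.
- In section 6.3.3 A, make the effect estimate the difference in restricted mean time to rule-out over 365 days, in days with a 95% CI, stratified by site and PTP. Keep rule-outs on the day of randomisation in the analysis as 0 days.
- Show the cumulative proportion ruled out by arm, and keep the stratified Cox hazard ratio as supportive.

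The cost is SAP wording and a standard procedure on data already collected. The small downside is that the estimate depends on the 365-day horizon, but the endpoint's one-year assessment already fixes it.
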